4.11 Safety Evaluation

TP-GDO-WW-016-01 Confidential Version 7.0 Effective Date: 28Aug13 Version Date: 28NOV2018

Related to: SOP-GDO-WW-019

Page 27 of 60

Unless otherwise specified, all safety summaries and analyses will be based upon the SAF as defined in Section 4.5

4.11.1 Subgroup analyses

Main safety data will be summarized by the same subgroups as for the efficacy analyses (see section 4.10.1.5). Baseline weight (<median, >= median) will be included in addition.

4.11.2 Extent of Exposure

Duration of exposure to study drug (days) is defined as date of last dose - date of first dose + 1, and will be summarized.

The following exposure summaries will be produced:

- A summary of exposure duration and study duration (days).
- A summary of the number of doses and total cumulative dose of study drug.

4.11.3 Adverse Events

Adverse events will be coded using MedDRA. All summaries will be sorted alphabetically by System Organ Class (SOC) and preferred term (PT), starting with the most frequent event. All adverse events reported in whole study will be reported in listings. For AEs, if the AE intensity is missing, the worst case (severe) will be assumed. If the drug relationship is missing, the worst case (drug related) will be assumed. In summaries, multiple occurrences of the same PT event in one individual will be counted only once.

The following summary tables of AEs will be provided:

- An overall summary of AEs will be presented. It will include the number and percentage
 of subjects with at least 1 AE, serious AE, AE leading to early discontinuation, adverse
 drug reaction, and severe AE and number of death.
- A summary of AEs by SOC and PT.
- A summary of AEs by Intensity, SOC and PT.
- A summary of AEs leading to discontinuations of treatment.
- A summary of AEs leading to dose interruption.
- A summary of adverse drug reactions (ADRs) by SOC and PT.
- A by-subject listing of all AEs.
- A by-subject listing of all AEs leading to discontinuation.
- A by-subject listing of all AEs leading to drug interruption.
- A by-subject listing of all ADRs.

TP-GDO-WW-016-01
Effective Date: 28Aug13
Related to: SOP-GDO-WW-019

Confidential Version 7.0 Version Date: 28NOV2018

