3 INVESTIGATIONAL PLAN

3.1 Overall Study Design and Plan

This is a multicenter randomized, double-blind, placebo-controlled parallel assignment study followed by an open-label extension (OLE) period. Patients will be randomized to two groups (2:1, Group A or B) and will receive subcutaneous (SC) SA237 (Group A) or placebo (Group B) at Weeks 0, 2, 4, and every 4 weeks (Q4W) thereafter. The randomization will be stratified by prior therapy for prevention of NMO/NMOSD attack (B-cell depleting therapy or immunosuppressants/others) and the most recent attack in the last one year prior to screening (first attack or relapse). If a patient was administered B-cell depleting therapies (e.g. anti-CD20 antibody [e.g. rituximab], anti-CD19 antibody) at least once in the year prior to baseline, the patient will be stratified into "B-cell depleting therapy group" and otherwise into the "immunosuppressants/others group" (e.g. oral corticosteroids, azathioprine, mycophenolate mofetil, cyclosporine, methotrexate, tacrolimus).

Patients who experience a protocol-defined relapse which is adjudicated by the Clinical Endpoint Committee (CEC) in the double-blind period or complete the double-blind period can enter the open-label extension period. The double-blind period of the study ends when the total number of CEC-confirmed protocol-defined relapses is 44. At the end of the double-blind period, the clinical cut-off date for the primary analysis will be on the day of the onset of the protocol defined 44th relapse (adjudicated by the CEC) or 1.5 years after the date of randomization of the last patient enrolled, whichever comes first. In the extension period, patients can receive open-label treatment with 120 mg SA237 SC at Weeks 0, 2, 4, and every 4 weeks (Q4W) thereafter, until commercial availability of SA237 or Sponsor's decision to discontinue the development program.

For patients who experience a relapse in the double-blind period, appropriate rescue therapy for relapse will be administered. For patients who experienced a relapse which is adjudicated by the CEC as a protocol-defined relapse, SA237 should start under stable disease conditions (i.e. Day 31 or later, where Day 1 is defined as the day of onset of a protocol-defined relapse confirmed by CEC). For patients who completed the double-blind

TP-GDO-WW-016-01 Confidential Version 7.0 Effective Date: 28Aug13 Version Date: 28NOV2018

[figure not shown]
Related to: SOP-GDO-WW-019 Page 8 of 60

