4.2 General Presentation Considerations

The analyses periods are defined as follows:

- Study duration of double blind period for efficacy analysis
 - Study duration of double-blind period starts on the day of the randomization. The double-blind period ends on the earliest day of 1) clinical cutoff date (CCOD), 2) the day before the first treatment in the extension period, 3) the end of the study, or 4) last contact for patients lost to follow up.
- Double blind period for safety analysis
 - Double blind period starts on the day of first dose of study drug. The double-blind period ends on the same day as the efficacy analysis.
- Study duration of SA237 exposure for safety analysis (for All SA237 analysis)
 - Study duration of SA237 exposure starts on the day of first dose of SA237. Study duration of SA237 exposure ends on the earliest day of 1) CCOD, 2) the end of the study, or 3) last contact for patients lost to follow up.

The definition of summaries by visit is as follows:

- Summaries by visit for double blind period
 - Baseline is defined as the latest data before or on the date prior to first administration with either placebo or SA237. Summarized visits except for baseline are defined as follows. Irregular visits such as unscheduled visit between week X, dose outside the visit window (DOW), extra visit at relapsing, and the end of the study are out of scope. Week X visits are

TP-GDO-WW-016-01 Confidential Version 7.0 Effective Date: 28Aug13 Version Date: 28NOV2018

Related to: SOP-GDO-WW-019

Related to: SOP-GDO-WW-019

directly used for categories of time. In other words, time window is not applied. If there are the same visits data, one representative assessment nearest to the scheduled visit day will be summarized.

- Summaries by visit for All SA237 analysis
 - Baseline is defined as the latest data before or on the date prior to first administration of SA237. Summarized visits except for baseline are defined as follows. Irregular visits such as unscheduled visit between week X, dose outside the visit window (DOW), extra visit at relapsing, and the end of the study are out of scope. Time window is applied as if visit schedules continue in the double-blind period. Middle of each specified day of visit will be used for the range of time window of each visit. One representative assessment nearest to the specified day of visit in time window of each visit will be summarized

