Continuous data will be summarized in terms of the mean, standard deviation (SD), median, minimum, maximum and number of observations, unless otherwise stated. The minimum and maximum will be reported to the same number of decimal places as the raw data recorded in the database. The mean, median and SD will be reported to one more decimal place than the raw data recorded in the database. In general, the maximum number of decimal places reported shall be four for any summary statistics.

For categorical parameters, the number and percentages of subjects in each category will be presented at the relevant time point. The denominator for percentage will be based on the number of subjects appropriate for the purpose of analysis. Unless otherwise noted, percentages will be presented to one decimal place. Percentages will not be presented for zero counts and 100% will be presented as an integer. The denominator for all percentages will be the number of subjects in that treatment group within the population of interest, unless otherwise noted. Missing category will only be displayed when there are missing data.

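### Apart from serious infections, no double-blind adverse event summary accounts for unequal follow-up, so crude percentages for events that accrue over time would look moderately higher on satralizumab if the drug prevents relapse

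*SAP*

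**What the plan says.** SAP 4.2 starts the double-blind safety window at the first dose and gives it the efficacy window's end: "The double-blind period ends on the same day as the efficacy analysis". That end is the earliest of the clinical cut-off, "the day before the first treatment in the extension period", the end of the study, or last contact for patients lost to follow-up. Under SAP 3.1, patients with a CEC-confirmed relapse may enter the extension, with satralizumab starting at "Day 31 or later, where Day 1 is defined as the day of onset of a protocol-defined relapse confirmed by CEC". The others enter only if they "or complete the double-blind period can enter the open-label extension period".

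SAP 4.11.3 begins: "An overall summary of AEs will be presented. It will include the number and percentage" of subjects with at least one AE, SAE, severe AE, adverse drug reaction or AE leading to discontinuation. The further AE and SAE tables in 4.11.3 and 4.11.4 are called summaries or summaries of incidence. The 4.2 default then applies: "The denominator for all percentages will be the number of subjects in that treatment group within the population of interest". Within a table, "multiple occurrences of the same PT event in one individual will be counted only once".

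Two items do use time. SAP 4.11.7 gives serious infections per 100 patient-years with an exact interval. SAP 4.11.2 lists "A summary of exposure duration and study duration (days"), but as a separate table. Protocol 6.6 plans numbers, percentages and incidence, with no person-time measure.

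**The concern.** Protocol 2.2 makes the safety objective a comparison with placebo. A crude percentage depends on how long each patient is watched as well as on the AE rate. Relapse shortens the watching, and preventing relapse is what the drug is meant to do. For events that accrue over time, the crude comparison therefore mixes any AE effect with the efficacy effect. At identical AE rates the arm that relapses less shows the higher percentage.

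The stake is misreading, in either direction. A follow-up artefact could be taken for a modest excess on satralizumab, or a real modest excess could be put down to longer follow-up with no planned analysis to settle it.

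**Working it through.** **Inputs from SAP 3.1 and 4.14.** 90 patients at 2:1 (60 satralizumab, 30 placebo); placebo relapse hazard 1.1295 per year; hazard ratio 1.0 for 2 months, then 0.25; 10% dropout at 2 years, i.e. −ln(0.9)/2 = 0.0527 per year; 33 months' accrual; cut-off at the 44th confirmed relapse or 1.5 years after the last randomization.

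**Assumptions not in the documents.** AE rates r of 0.1 to 0.5 per year, equal in both arms; accrual shape (uniform, or rising linearly); a gap g of 30, 60 or 90 days from relapse to extension (only the Day 31 minimum is given); every relapser enters the extension; a later hazard ratio of 0.5 as an alternative. Patients are counted under their double-blind treatment.

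**The plan's own figures.** Placebo ARR: 0.7 × 1.5 + 0.3 × 1.0 = 1.35. One-year relapse-free rate: exp(−1.1295) = 32.3%. Simulated log-rank power at 44 events is 0.83 to 0.84 (uniform accrual) or 0.81 to 0.82 (rising), so the stated 80% holds. Expected events at 33 + 5 months are 50.3 (uniform) or 44.1 (rising), so rising accrual is the shape that matches the plan.

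**Formula.** Window W = min(relapse time + g, dropout, cut-off). Crude percentage = mean of 1 − exp(−rW) over the arm.

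**Ratio of crude percentages, satralizumab over placebo, for r from 0.5 down to 0.1 per year:**

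| Later HR | Accrual | g = 30 days | g = 60 days | g = 90 days |
|---|---|---|---|---|
| 0.25 | rising | 1.28–1.36 | 1.23–1.31 | 1.19–1.26 |
| 0.25 | uniform | 1.32–1.43 | 1.26–1.36 | 1.22–1.31 |
| 0.5 | rising | 1.13–1.17 | in between | 1.09–1.12 |
| 0.5 | uniform | 1.17–1.21 | in between | 1.11–1.15 |

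Repeat runs agree to about 0.01. With a hazard ratio of 1.0 throughout, the ratio is 1.00 at every rate, so the effect comes only from follow-up.

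**Example (HR 0.25, rising, 60 days).** Mean window 0.73 years on placebo and 0.97 on satralizumab, a ratio of 1.33. At 0.1 per year: 6.9% against 9.0%; on 30 patients that is 2.1 against 2.7, a shift of 0.6. At 0.5 per year: 28.7% against 35.3%, or 8.6 against 10.6, a shift of 2.

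**At-least-one-AE row.** Protocol 1.2 reports AEs in 22 of 33 Phase 1b patients. Assuming a 16 to 24 week evaluation period (its length is not given), the rate is −ln(1 − 22/33) = 1.10 divided by 0.31 to 0.46 years, i.e. 3.6 to 2.4 per year. The ratio is then 1.02 to 1.10 at HR 0.25 and 1.01 to 1.05 at HR 0.5.

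**AE rate raised after relapse (HR 0.25, rising, 60 days).** If the rate after relapse is 2 to 3 times higher (assumed), the crude ratio falls to 1.09–1.21. The first-event patient-year rate ratio, which is 1.0 under a constant rate, becomes 0.87 to 0.93.

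**Events clustered early.** With an identical 20% risk confined to the first 8 weeks, crude percentages are about 19 to 20% in both arms. The patient-year rate ratio is 0.69–0.81 (HR 0.25) or 0.82–0.90 (HR 0.5).

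**Precision.** On about 20 placebo patient-years, one event gives 5.0 per 100 (95% CI 0.1 to 27.9) and ten events give 50 (24 to 92). In the example, the binomial SD of the arm difference is √(0.069×0.931/30 + 0.090×0.910/60) = 5.9 points at 0.1 per year, against a shift of 2.1. At 0.5 per year it is √(0.287×0.713/30 + 0.353×0.647/60) = 10.3 points, against 6.6.

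**The case against.** The strongest case is that this is a reporting preference. The tables carry no test or decision rule. Serious infection, the identified risk carried over from tocilizumab (protocol 5.1.1.1), already has a rate. Study duration is summarised, so the imbalance will be visible. The shift is smaller than chance variation between arms of this size. All of that stands, and it limits the weight of the point.

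The constant-rate assumption is also open to attack. The window runs past relapse to the extension, and in that stretch patients may receive steroids, immunoglobulin or apheresis (protocol 4.4.1). More placebo patients pass through it. If that raises AE rates, the crude imbalance shrinks and a patient-year rate starts to favour satralizumab. This stands too.

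Finally, a naive patient-year denominator could include time when AEs are not collected. Protocol 5.3.1 ends AE reporting at the Withdrawal Visit or Last Observation, 12 weeks after the last dose. Patients who withdraw because of relapse then have telephone follow-up to 24 weeks, for which Appendix 1, Table 6 schedules no AE recording. The fix has to respect this.

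Three stronger readings are tempting and are not supported. A reader might infer that every AE row, including the at-least-one-AE row, would be inflated by up to 40%; that row moves by at most about 10%. A reader might infer that the tables could hide harm through this mechanism; the bias runs against satralizumab. A reader might infer that patient-year rates are unbiased and should replace percentages; for early-clustered or post-relapse events they err in the drug's favour.

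**Conclusion.** The gap is real and the point holds as a modest reporting improvement. At the planned 44-event cut-off, with equal constant AE rates of 0.1 to 0.5 per year, crude percentages would be about 1.2 to 1.4 times as high on satralizumab at HR 0.25. With the accrual shape that fits 33 + 5 months, the range is about 1.2 to 1.37. At a later HR of 0.5 it is about 1.1 to 1.2.

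These figures rest on assumed AE rates, accrual shape and gap to the extension, and they shrink for common events and if AEs rise after relapse. Nothing here makes the safety comparison invalid. What remains is a possible misreading of overall rows such as SAEs, severe AEs and discontinuations, which a second measure would make easier to avoid.

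**What to change.** In SAP 4.11.3 and 4.11.4:

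- Keep the crude percentages.
- Add, by arm, first-event rates per 100 patient-years with exact 95% CI for the overall summary rows: any AE, SAE, severe AE, adverse drug reaction, AE leading to discontinuation. SOC-level rates are optional and will be imprecise; preferred terms need none.
- Count person-time from first dose to the earliest of first event, end of the 4.2 double-blind safety window, or end of AE collection under protocol 5.3.1, so that telephone-only follow-up is excluded.
- State that both measures are always shown together, and that patient-year rates can favour satralizumab for events clustered around the first doses or after relapse treatment.
- Protocol Version 10 (1.3) reports the double-blind period as completed. If its data are already unblinded, label the column as added afterwards.

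The cost is SAP wording and one extra column. No new data are needed: the window and a patient-year method already exist in 4.2 and 4.11.7. The downside is two measures that can disagree, which is why the note is needed.

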4.11.4 Deaths, Serious Adverse Events, and Other Significant Adverse Events

SAE will be provided by treatment group. SAE will be provided by subgroups The following summary tables of SAEs will be provided:

- A summary of incidence of serious AEs (SAEs) by SOC and PT.
- A summary of incidence of SAEs leading to discontinuation by SOC and PT.
- A by-subject listing for all deaths.

4.11.5 C-SSRS

The following will be presented for C-SSRS:

- A summary of C-SSRS.
- A by-subject listing of C-SSRS.

Scores reported in the "Baseline" and "Prior to study" pages of the CRF will be handled as baseline score. Scores reported in "Since Last Visit" and "Since Study Start" page of CRF will be summarized by visit when the data is recorded.

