CCSR- this sampling is optional and will require a separate signature on the informed consent

- Serum and plasma blood samples will be taken from the patients who consent to the procedure. 5 mL of serum blood and 4.5 mL for plasma blood.

During the double-blind period, when an extra visit at relapsing occurs, the following assessments are to be performed:

- Perform physical exam
- Record vital signs
- Laboratory test RBC, Hb, HCT, WBC, WBC differentiation, PLT, INR, fibrinogen, total protein, albumin, total bilirubin, ALP, AST, ALT, γ -GTP, LDH, total cholesterol, LDL, HDL, triglyceride, ferritin, BUN, creatinine, CK, Na, Cl, K, Ca, P, complement (CH50, C3, C4), uric acid, urinary glucose, urinary protein, urinary occult blood, urobilinogen

Safety

- Adverse events and concomitant medications will be monitored and recorded throughout the study

Efficacy

- EDSS/FSS

PK-PD

- Obtain PK sample
- Obtain PD sample includes IL-6, sIL-6R and hsCRP and anti-AQP4 antibody.
- Obtain plasmablasts sample.

CCSR- this sampling is optional and will require a separate signature on the informed consent

- Serum and plasma blood samples will be taken from the patients who consent to the procedure. 5 mL of serum blood and 4.5 mL for plasma blood.

Withdrawal visit (WD)

This visit should be performed for patients who withdraw from the study. Every effort should be made to conduct the visit at 12 weeks after the last dosing. Assessments to be performed at this visit are:

- Record body weight
- Perform physical exam
- Record vital signs
- ECG should be performed prior to blood draws.

- Perform Chest X-ray
- Perform pregnancy test for females of child-bearing potential. Serum or urine β -hCG [sensitivity of at least 25 mIU/mL] will be performed.
- Laboratory test RBC, Hb, HCT, WBC, WBC differentiation, PLT, INR, fibrinogen, total protein, albumin, total bilirubin, ALP, AST, ALT, γ -GTP, LDH, total cholesterol, LDL, HDL, triglyceride, ferritin, BUN, creatinine, CK, Na, Cl, K, Ca, P, complement (CH50, C3, C4), uric acid, urinary glucose, urinary protein, urinary occult blood, urobilinogen
- Hepatitis B viral DNA must be monitored in patients for whom a positive result for HBsAb is not clearly associated with vaccination against hepatitis B virus and HBV DNA is negative at screening or whom HBcAb is positive and HBV DNA is negative at screening.
- Perform C-SSRS

Safety

- AEs and concomitant medications will be monitored and recorded throughout the study

Efficacy

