Appendix 1: Schedule of Activities (cont.)

Table 6: Observation and Test Schedule in the Double-Blind Period (cont.)

- m) Body temperature, systolic and diastolic blood pressure and pulse rate are measured just before dosing and 15 min (± 5 min) and 60 min (± 5 min) after dosing in case of study treatment injection visit.
- n) Hepatitis B viral DNA must be monitored in patients for whom a positive result for HBsAb is not clearly associated with vaccination against hepatitis B virus and HBV DNA is negative at screening or whom HBcAb is positive and HBV DNA is negative at screening.
- o) Every 12 weeks.
- p) C-SSRS since last visit scale should be used.
- q) In the event that the study drug is not administered within the scheduled visit window and is subsequently administered outside the visit window. Minimum dosing interval should be 14 days.

DOW = dose outside the visit window, SFU = Safety follow-up, WD = Withdrawal visit, CCSR = Chugai Clinical Sample Repository.

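### C-SSRS has only a by-visit summary, whose scope rule leaves out dose-outside-window visits and, by implication, withdrawal visits; no any-time patient count per arm is specified (minor)

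*SAP*

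**What the plan says.** Suicidality measured by C-SSRS is a named safety outcome (Protocol 2.2 and 3.3.2; SAP 3.2.2), and Protocol 6.6 requires it to be summarised.

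SAP 4.11.5 (C-SSRS) lists two outputs: "A summary of C-SSRS" and "A by-subject listing of C-SSRS". Its one rule for post-baseline data covers two CRF pages, since last visit and since study start. Scores from either "page of CRF will be summarized by visit when the data is recorded".

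SAP 4.2 sets the scope of by-visit summaries. Irregular visits, meaning unscheduled visits, "dose outside the visit window (DOW), extra visit at relapsing, and the end of the study are out of scope". In the double-blind period the nominal week visits are "directly used for categories of time. In other words, time window is not applied". For categorical data, "the number and percentages of subjects in each category will be presented at the relevant time point".

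Protocol Appendix 1, Table 6 schedules C-SSRS at dosing visits, at DOW visits and at the withdrawal visit, but not at the extra relapse visit. Its footnote for the post-baseline form is "C-SSRS since last visit scale should be used". The withdrawal visit list in Protocol 4.5.3.2 repeats the instruction: "Perform C-SSRS".

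**The concern.** For most repeated measures, dropping an irregular visit from a by-visit table costs one reading of something that is measured again later. A since-last-visit form is different. It is the only form of its kind that covers its interval. If the form is out of scope, so is the interval.

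Percentages at separate visits also cannot be combined into a number of patients. The same patient may be positive at several visits, and different patients may each be positive once. The question a safety reader asks is how many patients in each arm had any ideation or behaviour on treatment. The specified table does not answer it.

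**Working it through.** There is no planned figure to reproduce. The check traces where the scale is collected and where it is summarised, and then sizes the gap.

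**Visit by visit, double-blind period**

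| Visit | C-SSRS collected (Protocol Table 6) | In by-visit summary (SAP 4.2) |
|---|---|---|
| Scheduled dosing visits | Yes | Yes |
| DOW | Yes | No, named as out of scope |
| Extra relapse visit | No | No, without effect here |
| Withdrawal visit | Yes | No, by implication |

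The withdrawal visit is not named in SAP 4.2. Two things point to exclusion. It is not a nominal week visit, and no window maps it to one. It also fits the end-of-study item in the list of irregular visits; the same section uses the end of the study as a patient-level end of the double-blind period.

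**What is lost.** After a DOW form, the next scheduled form asks only about the time since the DOW visit, so an event reported at the DOW visit is not asked about again. The withdrawal form is the last one. Protocol 4.5.2.3 aims for that visit 12 weeks after the last dose, so the form can cover up to about 12 weeks.

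**Contrast within the SAP.** Patient-level summaries over the whole period are planned for AST and ALT (maximum post-baseline level, 4.11.11), for ECG (incidence of treatment-emergent abnormal findings, 4.11.12) and for vital signs (patients abnormal during the double-blind period, 4.11.13). None is specified for C-SSRS.

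**Size**

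- Arms: 90 patients at 2:1 gives 60 and 30. One missed patient is 1/60 = 1.7 or 1/30 = 3.3 percentage points.
- Dropout hazard from the planned 10% over two years: -ln(0.9)/2 = 0.0527 per year.
- Double-blind follow-up at the 44th event was simulated with 90 patients, uniform accrual over 33 months, a placebo hazard of 1.1295 per year, and a hazard ratio of 1.0 for 2 months and 0.25 after that. The result is 18.2 patient-years on placebo and 56.4 on satralizumab, 74.6 in all.
- Expected withdrawals: 74.6 x 0.0527 = 3.9.
- Upper bound, if all 90 patients were at risk for two full years: 0.10 x 90 = 9.

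Neither document gives a rate of positive C-SSRS forms or of DOW visits, so the number of events missed cannot be computed.

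**The case against.** Several points on the other side have force.

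- **Other outputs carry the events.** Adverse events are sought at every contact up to the withdrawal or last observation visit (Protocol 5.3.1) and are counted once per patient per preferred term (SAP 4.11.3). The by-subject listing has no visit restriction. A reader might infer that an event recorded at a DOW or withdrawal visit disappears from reporting; the documents do not support that. The cover is incomplete, however. No rule in either document makes a positive C-SSRS an adverse event, suicidality is not among the events of special interest or the selected events (Protocol 5.2.3 and 5.2.4), and a listing gives no incidence by arm.
- **The wording is open.** The summary in SAP 4.11.5 is not defined, and its by-visit sentence could be read as covering every visit with data. A reader who infers that a patient-level count will never be produced goes too far; it is not specified. On the wider reading, 4.11.5 and 4.2 conflict and still need a clarifying sentence.
- **The since-study-start page may be cumulative.** If so, it could recover some events. Protocol 4.5.1.9 describes only the baseline and since-last-visit forms, and the CRF is not available here, so this cannot be settled.
- **The DOW gap is often short.** Protocol 4.5.2.2 asks sites to try to do the assessments at the scheduled visit even when the dose cannot be given.
- **The extension data are a separate matter.** A reader might carry the argument over to the All SA237 analysis. SAP 4.11.5 specifies no such C-SSRS table, safety summaries default to the safety set (SAP 4.11), and patients randomised to placebo have Day 1 reset at their first active dose (SAP 4.5).

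These points narrow the concern. They do not supply the missing patient-level table.

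**Conclusion.** The point holds in limited form and is minor. Following the stated rules, forms completed at DOW visits are outside the C-SSRS summary table. Forms completed at withdrawal visits are outside it too, on the reading of SAP 4.2 given above. No any-time post-baseline incidence by arm is specified.

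About 4 withdrawals are expected in the double-blind period under the planning assumptions. Some may be losses to follow-up with no withdrawal form, and most forms may be negative. Patients with recent active ideation or a past attempt within the stated limits are excluded at entry (Protocol 4.1.2). C-SSRS is descriptive here, and no efficacy conclusion depends on it. The case for change is that the gap affects a named safety outcome and costs little to close.

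**What to change.** In SAP 4.11.5 (C-SSRS), add one table by treatment group for the safety set with the number and percentage of patients with:

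- any post-baseline suicidal ideation;
- any post-baseline suicidal behaviour;
- each worst post-baseline category, against baseline.

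Use every C-SSRS form in the double-blind safety period, including those from DOW, unscheduled and withdrawal visits. State that the irregular-visit exclusion in SAP 4.2 does not apply to this table. Keep the by-visit table as supportive.

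The cost is a few lines of SAP text and one extra table from data already collected. No visit, form or procedure changes.
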